### **b) Contraception for Female Subjects of Childbearing Potential**

The inclusion of female subjects of childbearing potential requires the use of highly effective contraceptive measures. Women must have a negative serum pregnancy test at screening and a negative urine pregnancy test on the Day 1 visit prior to randomization. Pregnancy tests will be performed at monthly intervals thereafter. In the event of a delayed menstrual period (> one month between menstruations), a pregnancy test must be performed to rule out pregnancy. This is true even for women of childbearing potential with infrequent or irregular periods.

Female subjects must agree to use one of the following methods from screening until 35 days following the last dose of study drug.

- Complete abstinence from intercourse of reproductive potential. Abstinence is an acceptable method of contraception only when it is in line with the subject's preferred and usual lifestyle.

Or

- Consistent and correct use of 1 of the following methods of birth control listed below.

Intrauterine device (IUD) with a failure rate of < 1% per year

Tubal sterilization

Essure micro-insert system (provided confirmation of success 3 months after procedure)

Vasectomy in the male partner (provided that the partner is the sole sexual partner and had confirmation of surgical success 3 months after procedure)

- Female subjects, who wish to use a hormonally based method, must use it in conjunction with a barrier method; the barrier method is to be used either by the female subject or by her male partner. Female subjects who utilize a hormonal contraceptive as one of their birth control methods must have consistently used the same method for at least three months prior to study dosing. Hormonally-based contraceptives and barrier methods permitted for use in this protocol are as follows:

Hormonal methods (each method *must* be used with a barrier method, preferably male condom)

- Oral contraceptives (either combined estrogen/progestin or progesterone only)
- Injectable progesterone
- Implants of levonorgestrel
- Transdermal contraceptive patch
- Contraceptive vaginal ring

Barrier methods (each method *must* be used with a hormonal method)

- Male or female condom with or without spermicide
- Diaphragm with spermicide
- Cervical cap with spermicide
- Sponge with spermicide

All female subjects must also refrain from egg donation and in vitro fertilization during treatment and until at least 35 days after the last study drug dose.

### **3) Contraception Requirements for Male Subjects**

It is theoretically possible that a relevant concentration of study drug may be achieved in a female partner from exposure to the male subject's seminal fluid. Therefore, male subjects with female partners of childbearing potential must use condoms during study participation and for 90 days after the last study drug dose. Female partners of male study subjects should consider using one of the above methods of contraception as well. Male subjects must also refrain from sperm donation during treatment and until at least 90 days after the end of study drug dosing.

### **4) Unacceptable Birth Control Methods**

Birth control methods that are unacceptable include periodic abstinence (eg, calendar, ovulation, symptothermal, post-ovulation methods), withdrawal (coitus interruptus), spermicides only, and lactational amenorrhea method (LAM). Female condom and male condom should not be used together.

### **5) Procedures to be Followed in the Event of Pregnancy**

Subjects will be instructed to notify the investigator if they become pregnant at any time during the study, or if they become pregnant within 30 days of last study drug dose. Subjects who become pregnant or who suspect that they are pregnant during the study must report the information to the investigator and discontinue study drug immediately. Subjects whose partner has become pregnant or suspects she is pregnant during the study are to report the information to the investigator.

Instructions for reporting pregnancy, partner pregnancy, and pregnancy outcome are outlined in Section [7.7.2.1](#).

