**Steroid tapering must begin at Week 10 for subjects who are considered responders.**

CCI

Number of Subjects Planned: Up to 100

Target Population: Adults with moderately to severely active CD based on CDAI 200 to 450 (inclusive), with evidence of small bowel involvement and baseline MaRIA score of  $\geq$  7 in at least one of the following segments: terminal ileum (distal 15 cm of ileum, as measured from ileocecal valve), distal ileum (the portion of the ileum proximal to terminal ileum), and jejunum (small bowel located at the left upper quadrant)

Duration of Treatment: 24 weeks

Duration of Study: Up to 33 weeks

Diagnosis and  
Main Eligibility  
Criteria:

For a complete list of study inclusion and exclusion criteria,  
please refer to Section 4.

Main Eligibility Criteria

Subjects must meet all of the following inclusion criteria to be eligible  
for participation in this study:

- Males or non-pregnant, nonlactating females, ages 18 to 75 years, inclusive based on the date of screening visit
- Moderately or severely active CD as defined by screening CDAI 200 to 450 (inclusive)
- Minimum duration of CD of at least 6 months, documented by at least one of the following:

A histopathology report showing features consistent with CD  
as determined by the pathologist

Imaging consistent with diagnosis of CD or

Medical record documentation of or an ileocolonoscopy report  
showing features consistent with CD

- Presence of diseased SB segments on MRE with segmental MaRIA score of  $\geq 7$  in at least 1 of the following segments: terminal ileum, distal ileum, or jejunum
- Patients with additional colonic involvement of CD are permitted in study as long as SBCD is present
- Previously demonstrated an inadequate clinical response, loss of response to, or intolerance to at least 1 of the following agents (depending on current country treatment recommendations/guidelines):

Corticosteroids

- Active disease despite a history of an induction regimen of a dose equivalent to oral prednisone 30 mg daily for 2 weeks or intravenously (IV) for 1 week, OR
- Two failed attempts to taper steroids below a dose equivalent of 10 mg daily prednisone, OR
- History of steroid intolerance including, but not limited to, Cushing's syndrome, osteopenia/osteoporosis, hyperglycemia, insomnia, serious infections, depression, allergic reactions, mood disturbances, or any other condition that contributed to discontinuation of the agent

Immunomodulators

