#### **4.3. Exclusion Criteria**

Subjects who meet *any* of the following exclusion criteria are not to be enrolled in this study.

- 1) Pregnant or lactating females.
- 2) Males and females of reproductive potential who are unwilling to adhere to contraceptive guidance as outlined by [Appendix 7](#).
- 3) Females who may wish to become pregnant and/or plan to undergo egg donation or egg harvesting for the purpose of current or future fertilization during the course of the study and up to 35 days after the last dose of the study drug.
- 4) Male subjects unwilling to refrain from sperm donation during the study and for at least 90 days after the last dose of study drug.
- 5) Known hypersensitivity to filgotinib, its metabolites, or formulation excipients.
- 6) Presence of symptomatic or clinically significant (eg, obstructive or symptomatic) strictures or stenosis.
- 7) Presence of fistulae.
- 8) Evidence of short bowel syndrome.
- 9) Any other complication of CD that could preclude the use of CDAI to assess response to therapy or would confound the evaluation of benefit from treatment with filgotinib.
- 10) Claustrophobia to a degree that prevents tolerance of MRE scanning procedure (sedation is permitted at discretion of investigator).
- 11) Metallic implant of any sort that prevents MRE examination, not limited to but including aneurysm clips, metallic foreign body, vascular grafts or cardiac implants, neural stimulator, metallic contraceptive device, body piercing that cannot be removed, cochlear implant; or other contraindication to MRE examination.
- 12) Known hypersensitivity to gadolinium
- 13) Isolated colonic CD, or isolated CD that does not involve some segment of the small bowel.
- 14) Evidence of any other CD manifestation that might require imminent surgery or would possibly confound the evaluation of benefit from treatment with filgotinib.
- 15) Have any current or prior abscesses, unless they have been drained and treated at least 6 weeks prior to Day 1 and are not anticipated to require surgery.
- 16) History of major surgery or trauma within 30 days prior to screening.

- 17) Presence of ulcerative colitis, indeterminate colitis, ischemic colitis, fulminant colitis, or toxic mega-colon.
- 18) Dependence on parenteral nutrition.
- 19) History of total colectomy, subtotal colectomy, presence of ileostomy or colostomy, or likely requirement for surgery during the study.

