### **5.4. Prior and Concomitant Medications**

All medications taken up to 30 days prior to the screening visit through the end of study (30 days after the last dose of study drug) need to be recorded in the source documents and on the eCRF. At each study visit, the study center will record any and all concomitant medications taken by the subject since the last visit or during the visit (as applicable). All concomitant medications (prescription, peri-procedural medications, over-the-counter medications, including vaccines, vitamins, herbal, dietary supplements, and minerals) must be recorded in the concomitant therapy section of the eCRF.

Effective current therapies should not be discontinued for the sole purpose of participating in this study. Subjects may receive medications as supportive care or to treat AEs as deemed necessary by the Investigator or the subject's physician. Should subjects have a need to initiate treatment with any excluded concomitant medication, the Gilead Medical Monitor should be consulted prior to initiation of the new medication. In instances where an excluded medication is initiated prior to discussion with the Sponsor, the Investigator should notify Gilead as soon as he/she is aware of the use of the excluded medication.

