## **6.9. Post-Treatment Assessments**

All subjects must complete the post-treatment assessments 30 days after the last dose of study drug. CCI

- Symptom-directed PE
- Obtain body weight and vital signs (resting blood pressure, respiratory rate, pulse and temperature)
- Review AEs and concomitant medications
- Obtain blood samples (see Study Procedures Table [[Appendix 2](#)])
- Obtain urine sample for pregnancy test (for females of childbearing potential only)

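### Appendix 7 tells subjects to notify pregnancies for a shorter time after the last dose than the same protocol requires contraception: 5 days short for women, and an undefined post-dose period for partners of men

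*Protocol*

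**What the plan says.** **Notification.** Protocol Appendix 7 item 5 sets out what subjects will be instructed to do. A woman notifies the investigator if she becomes pregnant during the study, or "if they become pregnant within 30 days of last study drug dose". For men the sentence covers "Subjects whose partner has become pregnant or suspects she is pregnant during the study", with no time after the last dose. Item 5 then refers to Section 7.7.2.1 for the reporting of pregnancy, partner pregnancy and outcome.

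**Precautions in women.** Contraception runs "from screening until 35 days following the last dose of study drug" (Appendix 7 item 2b). The bar on egg donation and in vitro fertilization lasts "until at least 35 days after the last study drug dose" (same item). Exclusion criterion 3 in Section 4.3 uses the same limit: "up to 35 days after the last dose of the study drug".

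**Precautions in men.** Appendix 7 item 3 requires condoms during participation and for 90 days after the last dose, and bars sperm donation to at least day 90. Exclusion criterion 4 in Section 4.3 repeats the 90 days for sperm donation.

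**Investigator reporting.** Section 7.7.2.1 covers pregnancies in female subjects that are identified up to the end of the follow-up period after study drug. Partner pregnancies must be reported within 24 hours, with no end date. Serious adverse events that are adverse pregnancy outcomes after the study must also be reported.

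**End of study.** Section 3.8 defines it for the trial: 30 days after the last subject's last dose. Section 5.4 uses a per-subject end when it sets the medication-recording period: "through the end of study (30 days after the last dose of study drug". Section 6.9 puts the final visit at the same point: "All subjects must complete the post-treatment assessments 30 days after the last dose of study drug".

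**The concern.** The sponsor chose 35 and 90 days as the periods in which a conception should be avoided. A contraceptive failure inside those periods is one the sponsor would presumably want to hear about, yet the instruction to subjects stops earlier for women and names no post-dose period for men.

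After the day-30 visit the visible text schedules no further contact and no further pregnancy test. The investigator then learns of a pregnancy mainly from the subject, so even an open-ended reporting duty works only as far as subjects know to call. The subject matter is not trivial. Section 1.2.2.4 describes teratogenicity in rats and rabbits at exposures close to the human exposure at 200 mg, and the introduction to Appendix 7 says that no safety margin has been identified.

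What is at stake is the completeness of pregnancy follow-up. No efficacy endpoint, sample size or stopping rule depends on it.

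**Working it through.** **Inputs** (days after the subject's own last dose)

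| Item | Women | Men / partners | Source |
|---|---|---|---|
| Precautions end | 35 | 90 | Appendix 7 items 2b and 3; Section 4.3 |
| Subject notification ends | 30 | during the study, no day given | Appendix 7 item 5 |
| Final scheduled visit | 30 (±3) | 30 (±3) | Section 6.9; Appendix 2 |

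**Step 1. Does the plan's own duration fit an end at day 30 for each subject?** The Synopsis gives "Duration of Study: Up to 33 weeks". Screening 30 days + treatment 24 × 7 = 168 days + follow-up 30 days = 228 days, and 228 / 7 = 32.6 weeks. With the +3-day visit window, 231 / 7 = 33.0 weeks. The stated figure is reproduced, so it supports a per-subject end at about day 30.

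**Step 2. Women.** Gap = 35 − 30 = 5 days, that is 5/35 = 14% of the post-dose precaution period. It covers conceptions on days 31 to 35. The 30-day limit is written in item 5, so the visit window does not move it.

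**Step 3. Partners of male subjects.** Gap = 90 − (day on which the study ends for that man).

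- *Ends at the day-30 visit* (Sections 5.4 and 6.9): 90 − 30 = 60 days, or 57 to 63 across the ±3-day window. This is 60/90 = 67% of the precaution period.
- *Ends at the last dose*: 90 − 0 = 90 days.
- *Trial-level end* (Section 3.8): let d be the days from his last dose to the last dose given to any subject. Gap = max(0, 90 − 30 − d). With d = 0 it is 60 days, with d = 30 it is 30 days, and with d of 60 or more it is 0.

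**Step 4. Which reading does item 5 favor?** None fits cleanly. The separate 30-day limb for women adds something only if the study ends for her before day 30. If it ended at day 30 or at the trial-level date, the limb would be redundant, because the trial-level date is never earlier than a subject's own day 30. Applied to women, the trial-level reading would shrink the 5-day gap to max(0, 35 − 30 − d), but only by making the written 30-day limit pointless. Section 4.3 and Appendix 7 item 3 also count the 90 days in men separately from the study or from participation, which fits a per-subject end. The partner gap is therefore a range, not one number.

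**Step 5. Instruction against reporting rule.** Item 5 turns on when the woman *becomes* pregnant, while the female-subject clause in Section 7.7.2.1 turns on when the pregnancy is *identified*. If the follow-up period in that clause ends at the day-30 visit (an assumption, since the clause gives no day), a pregnancy that began by day 30 but was found later falls under item 5 and outside the clause. The partner clause has no such limit.

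**The case against.** The strongest reply is that the partner half is already handled. Item 5 refers to Section 7.7.2.1, which requires partner pregnancies to be reported with no end date and followed to their conclusion. That stands. A reader might infer that 60 of 90 days' worth of partner pregnancies would escape reporting. The documents do not support this: those days lack only an explicit prompt to the man, and an investigator who hears of such a pregnancy must report it. Nor is 60 a fixed figure. Section 3.8 is the only section headed as defining the end of the study, and it does so for the whole trial. The per-subject wording in Section 5.4 sits inside a medication-recording rule.

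Second, notification and contraception need not have equal length. A contraception period can carry a margin, and 30 days matches adverse event collection in Section 7.3.1 and the final visit. This is a fair defense of 30 days as a choice, but it does not explain why the partner clause has no post-dose period.

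Third, the female gap is small. Conception by day 30 is covered however late it is found, and Section 6.9 includes a pregnancy test at day 30. That also stands; only days 31 to 35 are left. Sections 7.3.2 and 7.7.2.1 catch relevant serious events after the study, though an uncomplicated pregnancy is not an adverse event under Section 7.7.2.1.

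Finally, the consent form was not available, and text in Sections 3.9 and 6.9 is redacted. Either may already tell subjects more.

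**Conclusion.** The point holds as a minor one. On the written 30-day limit, the instruction to women ends 5 days before their precautions do. The instruction to men leaves the post-dose period undefined. The shortfall is 60 days on the per-subject day-30 reading, up to 90 if the study ends at the last dose, and 0 to 60 on the trial-level definition. For partners the gap is confined to what men are told; the investigator's duty is already open-ended. For women the reporting clause in Section 7.7.2.1 also has a limit tied to identification.

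A reader might go further and infer that fetal harm would be missed. The documents do not show that. Appendix 7 item 3 describes exposure through semen as only a theoretical possibility, and nothing in the plan shows relevant exposure on days 31 to 35. The case for change rests on aligning the protocol with its own precaution periods at little cost. It assumes that the unseen consent and redacted text do not already close the gap.

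**What to change.** - **Appendix 7 item 5, women:** instruct them to notify any pregnancy occurring up to 35 days after their last dose.
- **Appendix 7 item 5, men:** instruct them to notify any partner pregnancy occurring up to 90 days after their own last dose. Counting from the man's own last dose removes the dependence on how the end of the study is defined.
- **Section 7.7.2.1, female-subject clause:** keep the present scope and add any pregnancy occurring up to 35 days after the last dose, whenever it is identified. The partner clause needs no change.

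With these changes the gap is 35 − 35 = 0 days for women and 90 − 90 = 0 days for partners. The cost is revised protocol and subject-instruction wording and possibly a few extra reports, with no added visits. Check the consent form and the redacted follow-up text first, since they may already cover part of this.

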### **Pregnancy Testing**

All females of childbearing potential will have urine pregnancy testing every 4 weeks (in clinic) during their study participation. If a urine pregnancy test is positive, the subject should stop study drug immediately, contact the investigator, and have a confirmatory serum pregnancy test in clinic.

**Appendix 8. Clinical Laboratory Assessment Table**

| Hematology  | Chemistry  | Urinalysis   | Other   |
|---|--|--|---|
| Hematocrit
Hemoglobin
Platelet count
Red blood cell (RBC) count
White blood cell (WBC) count
Differentials (absolute and percentage), including:
Lymphocytes
Monocytes
Neutrophils
Eosinophils
Basophils
Reticulocyte count
Mean corpuscular volume (MCV) | Alkaline phosphatase
Aspartate aminotransferase (AST)
Alanine aminotransferase (ALT)
Total bilirubin
Direct and indirect bilirubin
Total protein
Albumin
Bicarbonate
Blood urea nitrogen (BUN)
Calcium
Chloride
Serum creatinine
Creatinine clearance
CC&G
Glucose
Phosphorus
Magnesium
Potassium
Sodium
Creatine Phosphokinase (CPK) | Appearance
Blood
Color
Glucose
Leukocyte esterase
pH
Protein
Urobilinogen
Microscopy | Urine drug screen for:
Amphetamines
Cocaine
Barbiturates
Opiates
Benzodiazepines
C-reactive protein (CRP)
QuantiFERON® TB – Gold In-Tube Analysis (if required per inclusion criteria)
Serum immunoglobulin
Prothrombin Time (PT)
Partial thromboplastin time (PTT)
International Normalized Ratio (INR) |
| Serology  | Fasting lipids   | Stool  | Pregnancy   |
| Hepatitis B surface antigen (HBsAg)
Hepatitis B surface antibody (Ab)
Hepatitis B Core Ab
Hepatitis C Ab
HIV Ag/Ab  | Triglycerides
Total Cholesterol
High-density lipoprotein cholesterol [HDL-C]
Low-density lipoprotein cholesterol [LDL-C]  | Bacterial stool culture
C-Diff Toxin
Ova and Parasites (O&P)   | In females of childbearing potential:
Serum pregnancy
Urine pregnancy  |

CRF	case report form(s)
CSR	clinical study report
CTCAE	Common Terminology Criteria for Adverse Events
CV	cardiovascular
CVEAC	cardiovascular safety endpoint adjudication committee
DMC	data monitoring committee
ECG	electrocardiogram
eCRF	electronic case report form(s)
EQ-5D	EuroQol five dimensions
ET	early termination
FAS	Full Analysis Set
Gilead	Gilead Sciences, Inc.
HBV	Hepatitis B Virus
HCV	Hepatitis C Virus
HDL	high-density lipoprotein
HIV	Human Immunodeficiency Virus
HLGT	high-level group term
HLT	high-level term
HRQoL	health-related quality of life
hs-CRP	high-sensitivity C-reactive protein
IBD	inflammatory bowel disease
IBDQ	inflammatory bowel disease questionnaire
ID	identification
IM	intramuscularly
IV	intravenously

IWRS	interactive web response system
LDL	low-density lipoprotein
LLOQ	lower limit of quantification
LLT	lower-level term
LOCF	last observation carried forward
LOQ	limit of quantification
LTE	long-term extension
MACE	major adverse cardiovascular events
MaRIA	Magnetic Resonance Index of Activity
MDD	minimal detectable difference
MedDRA	Medical Dictionary for Regulatory Activities
MI	myocardial infarction
MMP-9	matrix metallopeptidase-9
MRE	Magnetic Resonance Enterography
MST	MedDRA search term
MTX	methotrexate
NLP	Natural Language Processing
NRI	non-responder imputation
O&P	ova and parasites test
OIs	opportunistic infections
PBMC	peripheral blood mononuclear cell
PBO	placebo
PK	pharmacokinetic
PO	orally
PR	rectally
PRO2	patient reported outcomes consisting of 2 items: abdominal pain severity and liquid stool frequency
PT	preferred term
PTM	placebo to match
PTx	Post-Treatment
Q1, Q3	first quartile, third quartile
RCE	relative contrast enhancement
SAE	serious adverse event
SAP	statistical analysis plan
SBCD	small bowel Crohn's disease
SD	standard deviation
SE	standard error
SF-36	short-form 36 health survey
SMQ	Standardised MedDRA Queries
SOC	system organ class
TEAE	treatment-emergent adverse event

TFLs	tables, figures, and listings
TNF α	tumor necrosis factor-alpha
ULN	upper limit of the normal range
US	United States
vfPBMC	viable frozen peripheral blood mononuclear cell
V-Day	visit day
VTE	venous thromboembolism
WHO	World Health Organization
WPAI	Work Productivity and Activity Impairment

DEFINITION OF TERMS

Clinical Remission by CDAI	CDAI score < 150 points
Corticosteroid-free CDAI Remission	CDAI < 150 with no steroid use for at least 4 weeks prior to Week 24 for subjects on steroids at baseline
Disease Worsening	A \geq 100 point increase in CDAI score from the Week 10 value and CDAI score \geq 220 points at 2 consecutive visits
Non-responder	Subjects who never achieves a \geq 70 point CDAI reduction from baseline or CDAI < 150 at any point up to and including Week 10
Minimal Detectable Difference (MDD) by MRE	For segments with baseline MaRIA score \geq 15, the MDD is 6.5 units. For segments with baseline MaRIA score < 15, the MDD is 4.0 units.
Segment with Active Disease	Segmental MaRIA score \geq 7
Segment with Presence of Ulcerative Lesions (Moderate to Severe Radiographic Disease Activity)	Segmental MaRIA score \geq 11
Segment with Mild Radiographic Disease Activity	Segmental MaRIA score \geq 7 but < 11
Segment Level MaRIA Remission	For segments with baseline MaRIA score \geq 7, a segmental MaRIA score < 7 at Week 24
Segment Level MaRIA Response	For segments with baseline MaRIA score \geq 11, a segmental MaRIA score < 11, or a decrease from baseline in segmental MaRIA score \geq MDD For segments with baseline MaRIA score < 11 (but \geq 7), a segmental MaRIA score < 7 or a decrease from baseline in segmental MaRIA score \geq MDD
Segment Level Disease Stable	For segments with baseline MaRIA score \geq 7, absence of segment level MaRIA response and: if baseline MaRIA score \geq 11, no increase in segmental MaRIA score \geq MDD if baseline MaRIA score < 11, a segmental MaRIA score < 11 For segments with baseline MaRIA score < 7, no segment level disease worsening
Segment Level Disease Worsening	An increase in segmental MaRIA \geq MDD with a segmental MaRIA score \geq 7 at Week 24, or a segmental MaRIA score \geq 11 at Week 24 while baseline MaRIA score < 11
Subject Level Small Bowel MaRIA Remission	MaRIA score of < 7 in each of 3 segments: terminal ileum = distal 15 cm of ileum, measured from ileocecal valve distal ileum = the portion of the ileum proximal to terminal ileum jejunum = small bowel located at the left upper quadrant
Subject Level Small Bowel MaRIA Response	All small bowel segments with baseline MaRIA score \geq 7 achieve segment level MaRIA response, with no segment level disease worsening in any other segment(s)
Subject with Stable Small Bowel Disease	At least 1 small bowel segment with baseline MaRIA score \geq 7 doesn't achieve segment level response, while no segment level disease worsening in any other evaluable small bowel segment(s)
Subject with Small Bowel Disease Progression	At least 1 small bowel segment demonstrates segment level disease worsening

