## DEFINITION OF TERMS

|  |   |
|--|---|
| Clinical Remission by CDAI   | CDAI score < 150 points   |
| Corticosteroid-free CDAI Remission   | CDAI < 150 with no steroid use for at least 4 weeks prior to Week 24 for subjects on steroids at baseline   |
| Disease Worsening  | A $\geq$ 100 point increase in CDAI score from the Week 10 value and CDAI score $\geq$ 220 points at 2 consecutive visits   |
| Non-responder  | Subjects who never achieves a $\geq$ 70 point CDAI reduction from baseline or CDAI < 150 at any point up to and including Week 10   |
| Minimal Detectable Difference (MDD) by MRE   | For segments with baseline MaRIA score $\geq$ 15, the MDD is 6.5 units.
For segments with baseline MaRIA score < 15, the MDD is 4 units.   |
| Segment with Active Disease  | Segmental MaRIA score $\geq$ 7  |
| Segment with Presence of Ulcerative Lesions (Moderate to Severe Radiographic Disease Activity) | Segmental MaRIA score $\geq$ 11   |
| Segment with Mild Radiographic Disease Activity  | Segmental MaRIA score $\geq$ 7 but < 11   |
| Segment Level MaRIA Remission  | For segments with baseline MaRIA score $\geq$ 7, a segmental MaRIA score < 7 at Week 24   |
| Segment Level MaRIA Response   | For segments with baseline MaRIA score $\geq$ 15, a segmental MaRIA score < 11, or a decrease from baseline in a segmental MaRIA score $\geq$ MDD.
For segments with baseline MaRIA score < 15 (but $\geq$ 7), a segmental MaRIA score < 11.   |
| Subject Level Small Bowel MaRIA Remission  | MaRIA score of < 7 in each of 3 segments: 

terminal ileum = distal 15 cm of ileum, measured from ileocecal valve

distal ileum = the portion of the ileum proximal to terminal ileum

jejunum = small bowel located at the left upper quadrant

 |
| Subject Level Small Bowel MaRIA Response   | All small bowel segments with baseline MaRIA score $\geq$ 7 achieve segment level MaRIA response, with no increase in MaRIA score $\geq$ MDD in any other evaluable small bowel segment(s)  |
| Subject with Stable Small Bowel Disease  | At least 1 small bowel segment doesn't achieve segment level response, while no $\geq$ MDD increase detected in any evaluable small bowel segment.  |
| Subject with Small Bowel Disease Progression   | At least 1 small bowel segment has MaRIA score $>$ 11, while $\geq$ MDD increase in MaRIA score in at least 1 small bowel segment.  |

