6.3.2. Analysis of the Secondary Efficacy Endpoints

For binary endpoints, the same statistical analysis methods described in Section [6.2.2](#) for analyzing the primary efficacy endpoint will be utilized.

Continuous endpoints will be summarized using descriptive statistics (n, mean, SD, median, Q1, Q3, minimum, maximum) by treatment group and analysis visit.

An analysis of covariance (ANCOVA) model that includes treatment (filgotinib 200 mg, filgotinib 100 mg, or placebo), stratification factors as fixed-effect factors, and baseline value as covariates will also be implemented. The estimated means of treatment effects and estimated differences in treatment effects between each filgotinib dose group and placebo will be presented with 90% CIs. Before the ANCOVA model is conducted, the following imputation will be performed:

- For change from baseline in segmental MaRIA score, if segmental MaRIA score is missing at Week 24, then corresponding segmental MaRIA score at baseline will be used to impute the missing value.
- For change from baseline in CDAI score, any missing CDAI component score will be imputed by LOCF method using the previous valid component score calculated at most recent analysis visit (eg, use the component score from Week 6 to impute missing component at Week 10, or use the component score from Week 18 to impute missing component at Week 24). If the component score from the most recent analysis visit is also missing, the missing value will be imputed with corresponding component score at baseline.

The observed mean change from baseline values for CDAI scores will be summarized and plotted over all analysis visits by treatment group.

In addition, subjects' small bowel disease status (remission, response, stable, and progression) based on MaRIA score will be summarized by treatment group for Week 24. A detailed definition of disease status in MaRIA score is provided in definition of terms.

CCI

CCI

A series of 12 horizontal black bars of varying lengths, decreasing from left to right. Each bar is preceded by a small black vertical tick mark.

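### The SAP's 'stable' and 'progression' definitions overlap: a subject whose only worsening small bowel segment was active at baseline meets both

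*SAP*

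**What the plan says.** SAP Section 6.3.2 plans that subjects' "small bowel disease status (remission, response, stable, and progression) based on MaRIA score will be summarized by treatment group for Week 24", and sends the reader to the SAP's Definition of Terms for the categories.

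- **Stable (subject level).** At least one small bowel segment with baseline MaRIA of 7 or more fails to respond, "while no segment level disease worsening in any other evaluable small bowel segment(s"). SAP Section 6.5 repeats this wording as a declared change from the protocol.
- **Progression (subject level).** "At least 1 small bowel segment demonstrates segment level disease worsening". Section 6.5 repeats this too. There is no exemption and no condition on baseline activity.
- **Worsening (segment level).** A rise of at least the minimal detectable difference (MDD) ending at 7 or above, or a score of at least "11 at Week 24 while baseline MaRIA score < 11". For baseline scores of 15 or more "the MDD is 6.5 units"; below 15 it is 4.0.
- **Stable (segment level).** Response must be absent. For baseline 11 or more there must also be "no increase in segmental MaRIA score" as large as the MDD; for baseline 7 to below 11, the Week 24 score must stay below 11.

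The protocol's Definition of Terms gave subject-level stable a different condition: no "MDD increase detected in any evaluable small bowel segment" of MDD size or more. It does not contain the word *other*.

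**The concern.** Stable and progression are opposite statements about the same subject, so they should not both be true. The SAP's stable rule looks for worsening only in segments *other* than the one that failed to respond. If that segment is itself the one that got worse, nothing in the stable rule catches it, while the progression rule does.

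For such a subject the text supports three outputs: stable, progression, or a count in both rows. The progression count is complete if it is taken from its own definition. The stable count depends on how the programmer reads *other*. With planned arms of 40, 40 and 20, one subject moved in or out of stable shifts that arm's percentage by 1/40 = 2.5 points on filgotinib or 1/20 = 5 points on placebo.

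**Working it through.** There is no plan figure to reproduce; this is a check of rules. All rules are from the SAP's Definition of Terms.

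**Step 1. Can an active segment both respond and worsen?**

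| Baseline | Response at Week 24 | Worsening at Week 24 |
|---|---|---|
| 11 or more | below 11, or fall of at least MDD | rise of at least MDD |
| 7 to below 11 | below 7, or fall of at least 4.0 | rise of at least 4.0, or score 11 or more |

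Every response limb requires a score below baseline, and every worsening limb a score above it. The two exclude each other, so a worsening active segment is always a non-responding active segment and can serve as the segment that the stable rule starts from.

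**Step 2. Examples** (terminal ileum / distal ileum / jejunum)

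| Baseline to Week 24 | Stable | Progression | Reason |
|---|---|---|---|
| 12→20 / 5→5 / 5→5 | yes | yes | rise of 8 ≥ 4.0; no other segment worsens |
| 20→27 / 12→8 / 3→3 | yes | yes | rise of 7 ≥ 6.5; second segment responds |
| 12→20 / 5→9 / 5→5 | no | yes | a second segment also worsens (rise of 4 to 9) |
| 12→12 / 5→9 / 5→5 | no | yes | only an inactive segment worsens |

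**Step 3. How far does the overlap reach?** Take the scores 0, 3, 5, 6.5, 7, 9, 10.5, 11, 13, 14.5, 15, 18, 21.5, 25 and 30 at baseline and at Week 24. One segment then has 15 × 15 = 225 pairs:

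- active at baseline: 84 responding, 42 worsening, 39 neither (165)
- inactive at baseline: 41 worsening, 19 not (60)
- not worsening in total: 84 + 39 + 19 = 142

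Three-segment subjects with at least one active segment: 225³ − 60³ = 11,174,625.

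Progression: 11,174,625 − (142³ − 19³) = 8,318,196.

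Exactly one worsening segment, active at baseline: 3 × 42 × 142² = 2,540,664. Direct coding of the rules gives the same number meeting both definitions, so all of these overlap and no other progression profile does.

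**Step 4. Other readings of *other*.**

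- *Wider*: other than all non-responding segments. Profiles with two or three worsening active segments and no worsening inactive one are added: 3 × 42² × 142 + 42³ = 825,552, giving 3,366,216.
- *Narrower*: the condition must hold starting from every non-responding active segment. The two remaining segments must then be responding or inactive and not worsening (84 + 19 = 103 pairs each): 3 × 42 × 103² = 1,336,734.

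The overlap changes in size under each reading but does not vanish.

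**Step 5. With *other* deleted.** Overlap of stable and progression: 0. Every profile falls in exactly one of response (1,085,868), stable (1,770,561) and progression (8,318,196), which sum to 11,174,625. Remission is always contained in response.

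**Step 6. The protocol rule.** Protocol stable forbids an MDD-size rise in any evaluable segment and protocol progression requires one, so they cannot overlap.

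These counts weight every profile equally. They show the logic and are not patient frequencies.

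**The case against.** **The intent can be recovered.** Segment-level stable already excludes worsening of the segment itself, progression captures any worsening segment, and the two labels are opposites in plain language. Many programmers would put such a subject under progression. The word looks carried over from the adjacent response definition, where it is harmless because every active segment must already have responded and so cannot have worsened. This is a fair account of how the wording arose, but the outcome still rests on the programmer setting aside a word that Section 6.5 presents as a deliberate modification.

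**A narrower reading shrinks the overlap.** With terminal ileum 12→12, distal ileum 12→20 and jejunum 5→5, a reader who starts from the terminal ileum finds another segment worsening and says not stable. That reading replaces the literal requirement of at least one qualifying segment with a requirement on every non-responding one. It still leaves the 12→20 / 5→5 / 5→5 subject in both categories. What stands is that the extent of the overlap depends on the reading; its existence does not.

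**The categories need not be exclusive.** Section 6.3.2 does not say they are, and remission sits inside response. Nesting of that kind is coherent, whereas calling one subject both stable and progressed is a contradiction.

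**The consequence is small.** This is correct. The trial plans no formal hypothesis testing, and the summary is descriptive.

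**Conclusion.** The concern holds as a minor drafting error. As written, every subject whose single worsening segment was active at baseline meets both stable and progression, and no precedence is stated. The SAP introduced this when it reworded the protocol's definition.

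The effect is confined to the stable count in the Week 24 disease status summary. Subject-level response and progression do not overlap, and the primary and listed secondary endpoints do not use stable.

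The share of real progressors affected cannot be derived from the documents. Under illustrative assumptions (active baselines uniform on 7 to 25, inactive on 2 to 7, mean change 0, SD of change 3 to 8 in active and 0 to 5 in inactive segments), the literal reading gave 13% to 100% of progressors with one active segment, 38% to 96% with two and 70% to 91% with three. The narrower reading gave about 5% to 35% with two and 2% to 12% with three, with no change for one. These ranges are too wide and too dependent on the assumptions to support a single percentage.

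**What to change.** Delete *other* from the subject-level stable definition in the SAP's Definition of Terms and from its repetition in Section 6.5, so that the no-worsening condition covers every evaluable small bowel segment. No precedence order is then needed; remission can be shown as a subset of response.

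The cost is one word in two places, with no new data. The change does not settle how subjects without Week 24 segment scores enter the status summary; that needs its own sentence.
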